Investigated procedure	
It is planned to study the initial and long-term results of left ventricle reverse remodeling in patients with aortic regurgitation, depending on the strategy chosen for the correction of functional mitral regurgitation and its severity.

Duration of observation	12 months after surgical treatment
Methods of statistical evaluation	
The determination of the significance of differences between quantitative data of unrelated samples will be carried out using the Student's t-test under the condition of normal distribution; in the case of non-normal distribution, the Mann-Whitney test, White's test, Van der Waerden test, and Kolmogorov-Smirnov test are planned to be used. In the case of analyzing the significance of differences in quantitative data in related samples with a normal distribution, the paired Student's t-test is planned to be used; in the case of non-normal distribution, the Wilcoxon test and sign test will be used. Qualitative data analysis will be performed using the χ^2 test and the McNemar test. To assess the reliability of the relationship between quantitative data, regression analysis, Pearson's correlation coefficient, Spearman's rank correlation coefficient, and Kendall's correlation coefficient are planned to be used. Descriptive and analytical statistical methods will be finalized after analyzing the sample size. To eliminate the influence of differences in baseline clinical parameters on the study outcome, a propensity score matching analysis (PSM) is planned between the ordinary 'Unmatched' groups using the nearest neighbor matching method for 1:1 pair matching.
 
Demographic data and clinical indicators will be presented using descriptive statistics (absolute indicators and percentage shares for categorical variables, or mean \pm standard deviation for normally distributed continuous variables; for continuous variables with non-normal distribution, the median and interquartile range will be specified). The significance of differences in repeated measurements will be analyzed using ANOVA.

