Sample size	
Considering a clinically significant difference in left ventricle volumes 12 months after surgery, equal to 15 ml/m^2, with a power of 80% and alpha of 5%, the sample size should be at least 64 patients in each group.
 
The sample size usually depends on the standard deviation, which is determined based on the results of similar studies or, more often, a pilot study. Approximate indicators will be obtained by February 2024 after analyzing the RCHC sample within the framework of the dissertation research.

--------------------	---

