11.1 General Provisions

A multicenter controlled comparative prospective cohort study is planned.

It is known that chronic aortic valve insufficiency leads to significant remodeling of the left ventricle and development of functional mitral regurgitation. On one hand, residual mitral regurgitation may complicate the postoperative period by increasing the preload on the left ventricle; however, a dilated left ventricle after surgical correction of the aortic defect still requires supraphysiological preload during the most vulnerable period of early rehabilitation. As the volume of the left ventricle regresses, functional mitral regurgitation is also capable of regressing. A significant scientific task is to address the role of functional mitral regurgitation in the reverse remodeling of the left ventricle after correction of chronic aortic valve insufficiency.

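### 1:1 propensity matching is the only stated confounder control, but 120 patients cannot supply both good matches and 64 per group

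*Protocol*

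**What the plan says.** The Protocol, section 11.1, states: "A multicenter controlled comparative prospective cohort study is planned". No randomisation is described. Section 7 (Investigated procedure) says that results will be studied "depending on the strategy chosen for the correction of functional mitral regurgitation and its severity", and section 9.1 says that the surgeon faces the decision on the mitral valve. The groups therefore arise from clinical choice.

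Section 7 (Methods of statistical evaluation) gives one answer to the resulting confounding: "To eliminate the influence of differences in baseline clinical parameters on the study outcome, a propensity score matching analysis (PSM) is planned". As to how the pairs will be formed, the only specification offered is: "using the nearest neighbor matching method for 1:1 pair matching". In the same row, regression is listed only for relationships between quantitative variables, not for adjusting the comparison of groups. The row also says: "Descriptive and analytical statistical methods will be finalized after analyzing the sample size".

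On size, section 7 gives 120 patients in total. The sample size row reads: "Considering a clinically significant difference in left ventricle volumes 12 months after surgery, equal to 15 ml/m^2". For that difference, at the usual 80% power and 5% alpha, its conclusion is: "the sample size should be at least 64 patients in each group". It makes no allowance for patients lost in matching.

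**The concern.** Patients whose mitral valve is corrected are likely to differ at baseline from those whose valve is left alone, above all in degree of mitral regurgitation and left ventricular size. Both may bear on volume at 12 months. One-to-one matching without replacement improves balance by discarding patients who have no close counterpart, so it needs a surplus in at least one group. This plan has none.

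The likely result is either a comparison labelled 'matched' that is still largely confounded, or a cleaner one with far fewer patients than the stated calculation assumes. Main objective 5 in section 7 is a clinical protocol for simultaneous mitral surgery, so an error in either direction could carry into practice recommendations.

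**Working it through.** **Inputs from the protocol (section 7):** difference 15 ml/m², power 80%, alpha 5%, at least 64 per group, 120 in total.

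**Assumptions:** two groups; two-sided alpha; SD about 30 ml/m² (none is stated); one normally distributed baseline confounder; all 120 patients analysed, which is a best case because section 11.2.3 removes some patients after surgery.

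**1. The stated 64.** n per group = 2 × SD² × (1.96 + 0.8416)² / 15². With SD = 30 this is 2 × 900 × 7.849 / 225 = 62.8, so 63; the t-test version gives 63.8, so 64. SD 25 gives 44 and SD 35 gives 86. Solving back from 64 gives SD = 15 / (2.8016 × √(2/64)) = 30.3. The figure fits an SD of about 30 but cannot be confirmed without one.

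**2. The reserve.** 2 × 64 = 128, which exceeds 120. The number of 1:1 pairs without replacement cannot exceed the smaller group, so from 120 patients it is at most 60.

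**3. Equal groups, everyone paired.** If each patient is used once and none is dropped, the mean of the within-pair differences equals the difference of the two group means. This is an identity: the estimate and every baseline mean difference are unchanged.

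**4. Other splits of 120.** Simulation: true imbalance 0.5 SD, logistic propensity score, greedy nearest neighbour without replacement, no pair dropped. Power in m pairs = Φ(15 / (30 × √(2/m)) − 1.96), an unpaired approximation. Power with all patients replaces 2/m by 1/n₁ + 1/n₀.

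| Split | Imbalance before (SD) | After matching (SD) | Pairs | Power in pairs | Power, all 120, before any cost of adjustment |
|---|---|---|---|---|---|
| 60 v 60 | 0.48 | 0.48 | 60 | 78.2% | 78.2% |
| 56 v 64 | 0.49 | 0.30 | 56 | 75.4% | 78.0% |
| 50 v 70 | 0.51 | 0.18 | 50 | 70.5% | 77.0% |
| 40 v 80 | 0.53 | 0.08 | 40 | 60.9% | 73.3% |
| 30 v 90 | 0.49 | 0.04 | 30 | 49.1% | 66.0% |

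**5. Near-equal groups, poor matches dropped.** An illustrative caliper of 0.2 SD of the logit (not in the protocol), applied at 60 v 60, leaves about 46, 43 or 39 pairs for a true imbalance of 0.3, 0.5 or 0.8 SD. Residual imbalance is below 0.01 SD. Power by the same formula is 66.9%, 64.0% or 59.8%.

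**6. Sensitivity to the SD.** With 50 pairs, power is 85%, 70.5% or 57% at SD 25, 30 or 35. With 30 pairs it is 64%, 49% or 38%. The SD 25 values do not fit the protocol's own 64, since that SD would need only 44 per group.

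**The case against.** The strongest reply is that the protocol names only a method and a ratio. A caliper, a common-support rule, replacement and balance checks are details commonly left to a statistical analysis plan, which is not shown, and the methods are said to be open to finalisation. That stands, and it rules out several stronger readings that a reader might infer:

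- *That the plan is matching without a caliper.* The text is silent; it does not exclude one.
- *That equal groups are planned, so the matched set is simply the unmatched set.* The 64 is a minimum per group, not an allocation ratio, and the split will follow clinical choice. Step 3 is a limiting case. With clearly unequal groups, matching does remove most of the imbalance (0.08 SD left at 40 v 80).
- *That overlap between strategies is known to be poor.* No figure supports this. Section 9.1 frames the question around moderate regurgitation, where both strategies may be realistic.
- *That the bias has a known size in ml/m².* Any such figure needs assumed strengths of confounding that the documents do not give.

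Matching with replacement is also not excluded. In the simulation at 64 v 64 it lowers the imbalance from 0.49 to 0.02 SD. It does so by reusing some patients, so fewer distinct patients carry the comparison, and the wording about pairs reads more naturally as without replacement.

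The reply does not meet the constraint on numbers. A later plan can add a caliper or a balance rule, but it cannot raise 120 patients to 64 matched pairs. Finalising methods after looking at the sample also leaves the choice of rule until group sizes may already be known.

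**Conclusion.** The point holds as a conflict between the stated method and the stated numbers, not as a complaint about missing detail. No split of 120 lets 1:1 matching without replacement retain 64 patients per group. Near-equal splits with nearly everyone paired keep about 60% (0.30/0.49) to 100% of the imbalance. The routes that control the imbalance leave about 30 to 50 pairs, with power of about 50 to 70%.

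The ceiling of 60 pairs and the equal-group identity follow from arithmetic. The residual imbalances and pair counts depend on the simulated single confounder and, in step 5, on the illustrative caliper. The power figures depend on the assumed SD of 30 ml/m² and ignore any gain from correlation within pairs.

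Separately, 'eliminate' is too strong under any matching rule: matching can at best balance measured covariates.

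**What to change.** In section 7 (Methods of statistical evaluation):

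- Make the main confounder-controlled comparison one that keeps all enrolled patients: either a regression-adjusted comparison or a propensity overlap-weighted one, on at least baseline end-diastolic volume and degree of mitral regurgitation, with robust standard errors. Choose which before group outcomes are examined.
- Keep 1:1 matching as a supportive analysis, interpreted only if covariate balance in the matched set is shown.
- Replace 'eliminate' by 'reduce measured'.

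In section 7 (Sample size), state that the 64 per group and 80% power do not apply to the matched set, and reconcile 64 per group with the total of 120.

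The cost is protocol wording and routine analysis code. Echocardiography is already scheduled at Examination 1, so no new data are needed. There are downsides. A weighted estimate applies to patients for whom both strategies are realistic, and an adjusted one depends on the model. Neither deals with unmeasured confounding. Neither restores 80% power by itself: before any loss from weighting or gain from adjusting for baseline volume, 120 patients give at most about 78% at SD 30.

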6. HISTORY OF CHANGES

Version	Approval Date	Summary of Changes
Version 1.0	01.11.2023	Initial Draft
Version 1.1	20.03.2024	Changes made regarding the development of the information booklet

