10.2 Study endpoints

Primary endpoints:

1. *Reduction of the left ventricle end-diastolic volume at 3 and 12 months after surgical correction of aortic regurgitation*
2. *Freedom from readmission for heart failure related conditions 12 months after surgery*

Secondary endpoints:

1. Patient quality of life according to the EQ-5D-5L questionnaire results.

Exploratory endpoints:

1. Left ventricle ejection fraction at 3 and 12 months after surgical correction of aortic regurgitation

2. Diastolic function of the left ventricle based on echocardiography results, assessed preoperatively and at 3 and 12 months after surgical correction of the aortic regurgitation (mean E/e', DT)
3. Indexed to BSA volume of the left atrium (according to transthoracic echocardiography results) preoperatively, as well as at 3 and 12 months after surgical treatment

*BSA – body surface area, calculated using the Mosteller formula

11. Study design

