SAX BASE (CWD)	TV Vmax TR Vmax TVA PV Vmax PV Gmax PV Gmean PVA EDPR	
 • Tricuspid stenosis • Tricuspid regurgitation • Pulmonary stenosis • Pulmonary regurgitation • RVOT obstruction 	
SAX BASAL/MV (2D)	MVA (planimetry)	
 • Prolapse/elongation of leaflets. • Myxomatous/thickening/calcification with/without restriction of excursion. • Local contractility disorder at the basal level 	 

Study protocol

SAX LV (MID/APEX) (2D)		Hypo-, a-, dyskinesia of the walls. Dilation of the right ventricle	
---------------------------------------	--	--	--

Study protocol

A4CV (2D)	
EDVi ESVi EF LV LAVi RVD1 RVD2 RAsax RALax RAA RAVi
 
Normal values: EDVi (female <61 ml/m², male <74 ml/m²) ESVi (female <24 ml/m², male <31 ml/m²) EF LV (female >52%, male >54%) LAVi (<34 ml/m²) RVD1 (25-41 mm) RVD2 (19-35 mm) RALax (<53 mm) RAsax (<44 mm) RAA (<18 cm²) RAVi (female 15-27 ml/m², male 18-32 ml/m²)
 
Note: LAV is calculated using the disk summation method RAV is calculated using the area-length method
		
A4CV (M-mode)	
TAPSE
 
Normal value: TAPSE >17 mm
	
Right ventricular dysfunction
	

A4CV (CFD)		
• Mitral stenosis• Mitral regurgitation• Tricuspid stenosis• Tricuspid regurgitation• Atrial septal defect• Ventricular septal defect	
A4CV (PWD)	VE MV VA MV E/A MV DT MV Adur VE TV VA TV E/A TV DT TV S D ARdur	
• Diastolic dysfunction of the left ventricle• Diastolic dysfunction of the right ventricle 
Normal values: E/A MV 1.0-1.5 DT MV 160-220 msec S>D AR<150 msec Adur<ARdur
	
A4CV (CWD)	MV Vmax MR Vmax MVA TV Vmax TR Vmax TVA RVSP/SPAP	
• Mitral stenosis• Mitral regurgitation• Tricuspid stenosis• Tricuspid regurgitation• Pulmonary hypertension	

Study protocol

A4CV (TDI PW)	e' lat E/e' lat e' med E/e' med E/e' avg	Diastolic dysfunction of the left ventricle Normal values: e' lat >10 cm/s e' med >7 cm/s E/e' lat <13 cm/s E/e' med <15 cm/s E/e' avg <14 cm/s	
A5CV (2D)		
• Mitral stenosis• SAM with/without LVOT obstruction• Aortic sclerosis/stenosis• Dilation of chambers• Local contractility of the ventricular walls	
A5CV (CFD)		
• LVOT obstruction• Mitral stenosis• Mitral regurgitation• Aortic stenosis• Aortic valve insufficiency• Ventricular septal defect	

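### The synopsis plans 120 patients, but its own calculation needs at least 128 for two groups, and the SD behind that calculation is not given

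*Protocol*

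**What the plan says.** All the planning figures stand in Section 7 (Protocol Synopsis).

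- **Number of study subjects:** 120. The entry does not say whether these are enrolled or evaluable patients.
- **Sample size, difference:** the entry begins "Considering a clinically significant difference in left ventricle volumes 12 months after surgery" and sets that difference at 15 ml/m².
- **Sample size, result:** "with a power of 80% and alpha of 5%, the sample size should be at least 64 patients in each group".
- **Sample size, SD:** none is given. The entry notes that the sample size usually depends on the SD and adds "Approximate indicators will be obtained by February 2024 after analyzing the RCHC sample".
- **Statistical methods:** two-sample tests for unrelated groups, and a propensity-score analysis "using the nearest neighbor matching method for 1:1 pair matching".

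Section 6 dates version 1.1 to 20.03.2024. Its only logged change is "Changes made regarding the development of the information booklet".

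Section 10.2 gives the first primary endpoint as "Reduction of the left ventricle end-diastolic volume at 3 and 12 months after surgical correction of aortic regurgitation". It does not say whether that volume is indexed to body surface area. The same section does state indexing for the left atrium ("Indexed to BSA volume of the left atrium").

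**The concern.** Two entries in one synopsis give different sizes for the same study. The 80% power claim is attached to 64 per group, and 120 patients cannot supply 64 in each of two groups. A reader therefore cannot tell which figure governs recruitment, or whether the power claim applies to the study as planned.

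Two gaps make this harder to resolve. Without an SD, the 64 cannot be verified. And the calculation concerns an unnamed left ventricular volume in ml/m² at 12 months, whereas the primary endpoint is the reduction in end-diastolic volume at 3 and 12 months, with no scale stated. The power for that endpoint cannot be read from the text.

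**Working it through.** **1. The contradiction needs no SD.** Two groups: 2 × 64 = 128, and 128 − 120 = 8 patients short. Three groups would need 3 × 64 = 192. Under 1:1 matching, a split of k and 120 − k gives at most min(k, 120 − k) pairs, which is never more than 60. The matched comparison therefore cannot reach 64 per group.

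**2. Trying to reproduce the 64.** Stated inputs (Section 7): difference Δ = 15 ml/m², power 80%, alpha 5%. Not stated: SD and sidedness. With the normal approximation,

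n per group = 2 × SD² × (z for alpha + z for power)² / Δ²

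Solving for the SD at n = 64, two-sided: SD = 15 × √(64/2) / (1.960 + 0.842) = 30.3. The t-test gives 30.06. So 64 fits an SD of about 30, a standardised difference of 15/30 = 0.5. A one-sided test would fit an SD of about 34. These SDs are back-solved and are not in the protocol. The 64 is not shown to be wrong, only uncheckable.

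**3. Effect of 60 instead of 64 per group.** For each method, the table gives the SD interval over which 64 is the smallest n per group with 80% power, and the power at 60 per group across that interval.

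| Method | SD interval | Power at 60 per group |
|---|---|---|
| t-test, two-sided | 29.82–30.06 | 78.0%–77.4% |
| t-test, one-sided | 33.67–33.94 | 78.3%–77.7% |
| Normal, two-sided | 30.05–30.29 | 78.1%–77.4% |
| Normal, one-sided | 33.86–34.13 | 78.3%–77.7% |

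The loss is about 2 to 3 points whichever method was used. At SD 30 with a two-sided t-test, power is 80.1% at 64 and 77.5% at 60 per group. The difference detectable with 80% power rises from 15.0 to 15.5 ml/m².

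**4. Effect of the unknown SD** (two-sided t-test, Δ = 15, equal groups, unpaired).

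| Assumed SD | Power at 60 per group | Power at 64 per group | Total N for 80% |
|---|---|---|---|
| 25 | 90% | 92% | 90 |
| 30 | 77.5% | 80.1% | 128 |
| 35 | 64% | 67% | 174 |
| 40 | 53% | 56% | 226 |

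The break-even SD for 120 patients is 29.09: at or just below it they reach 80%, above it they do not.

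**5. Uneven groups or unmatched patients** (SD 30, two-sided unpaired t-test). A 50/70 split of 120 gives 76.4% and a 40/80 split 72.6%. Fifty matched pairs give 69.7%. These splits are illustrations; the protocol forecasts none.

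**6. Dates.** The pilot figures were due by February 2024 and version 1.1 is dated 20.03.2024. The current text thus still promises an overdue input for a number it already states. The change log does not show whether the figures were obtained.

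**7. Variable.** Appendix 2 (Section 22.2) lists indexed end-diastolic volume among the apical four-chamber measurements ("EDVi ESVi EF LV LAVi RVD1 RVD2"), and 12 months is one of the two endpoint times. The powered variable may therefore be the primary endpoint on an indexed scale, but the text does not say so.

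**The case against.** The strongest reply is that little turns on this. The gap is 8 patients, 2 to 3 points of power and 0.5 ml/m² in the detectable difference. The wide power range in step 4 comes from the unknown SD, not from 120 against 128: at 64 per group the same SDs give 92% down to 56%. Both points are right, and they limit the seriousness.

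Second, 120 may be enough. With equal groups and an SD just under 29.09 it reaches 80%. That is true of the study's actual power, but the protocol's own claim remains tied to 64 per group.

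Third, the 64 is not said to apply to the matched set, and matched pairs could be analysed as pairs. At SD 30, a paired t-test on 60 pairs gives 81% power with a within-pair correlation of 0.1 and 85% with 0.2. So falling short of 64 pairs does not by itself prove power below 80%. The protocol does not specify a paired analysis of the matched set, and this leaves the two stated numbers unreconciled.

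Fourth, the protocol openly says the SD is pending, sidedness is often left to an analysis plan, and the volume mismatch may be only loose labelling. These points stand as mitigation. Disclosure does not make the 64 verifiable, and the date for supplying the SD had passed. Figure 1, the sample-formation scheme, is not shown, so no weight is placed on the lack of a visible allowance for losses.

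**Conclusion.** The point holds. The synopsis states 120 patients and a calculation that needs at least 128, and no readable text reconciles them. This should be fixed, though its direct consequence is small: 77.4% to 78.3% power rather than 80%, if 64 per group is the true minimum. Those powers assume two equal groups, an unpaired comparison, no covariate adjustment and no loss of patients. The number of groups is inferred from the two-sample tests and 1:1 matching; more groups would widen the gap.

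The larger uncertainty is the SD, without which neither the 64 nor the power at 120 can be checked. The link between the powered volume and the primary endpoint is unclear rather than contradictory, and is a secondary point.

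**What to change.** The least costly route is to keep 120 and correct the sample size entry: state the SD actually used and its source, replace the 80% with the power that 120 patients give at that SD, and delete the sentence awaiting figures by February 2024. Possible wording:

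*Assuming an SD of [value, source] for [left ventricular volume variable, scale, time point], a difference of 15 ml/m², a [one-/two-]sided alpha of 5% and [test], [n] evaluable patients per group ([N] enrolled in total) give [x]% power.*

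The SD has to come first, because it determines [x] and could move the required total either way. While the entry is open, it would help to say whether the total means enrolled or evaluable patients, and to use the same volume variable, scale and time point here and in Section 10.2.

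The alternative is to keep 80% power at 64 per group and raise the number of subjects to at least 128.

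Keeping 120 costs a wording change, and the stated power may then fall slightly below 80%. The alternative costs at least 8 more patients. Under Section 15.1 either change needs the written agreement of the principal investigator and the local ethics committee.

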9. INTRODUCTION

9.1 Introduction and Research Hypothesis

During surgical intervention for aortic valve insufficiency accompanied by hemodynamically significant functional mitral regurgitation, the surgeon faces the question of whether intervention on the mitral valve is necessary. Secondary MR of varying degree is found in 60%-75% of patients who have undergone aortic valve replacement. [1]

We hypothesize that the chosen strategy regarding moderate mitral regurgitation during the correction of aortic valve lesion in patients with significant left ventricular remodeling plays a crucial role in the course of reverse LV remodeling when assessed by transthoracic echocardiography 12 months post-surgery.

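### The stated 80% power fits two complete, unmatched groups of 64; it is not assured for the planned 1:1 propensity-matched comparison

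*Protocol*

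**What the plan says.** The Sample size row of the protocol synopsis (section 7) takes a "clinically significant difference in left ventricle volumes 12 months after surgery, equal to 15 ml/m^2", and concludes that "with a power of 80% and alpha of 5%, the sample size should be at least 64 patients in each group". No SD is given. The row remarks that "The sample size usually depends on the standard deviation" and leaves its value to later data. It does not mention matching, unequal groups, missing echocardiograms or post-operative exclusions.

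Other parts of the protocol bear on how many patients enter the comparison:

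- **Design (11.1).** "A multicenter controlled comparative prospective cohort study is planned". No allocation ratio is fixed. Section 9.1 describes the setting as one where "the surgeon faces the question of whether intervention on the mitral valve is necessary".
- **Adjustment (synopsis, Methods of statistical evaluation).** Baseline differences are to be handled by propensity score matching "using the nearest neighbor matching method for 1:1 pair matching". The same row lists t-tests for unrelated and for related samples. Regression appears only for relationships between quantitative variables.
- **Removal after surgery (11.2.3).** Three events in the first 12 months exclude a patient: an acute coronary event, a need for resynchronisation or permanent right ventricular pacing, and repeat cardiac surgery.
- **Enrolment (synopsis, Number of study subjects).** 120 patients.

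**The concern.** The power statement and the adjustment method describe different data sets. The calculation supposes 64 analysed patients on each side. Matching 1:1 keeps at most as many pairs as the smaller group has patients, less those without an acceptable match and those without a 12-month volume. Nothing in the sample-size row says whether 64 counts enrolled, complete or matched patients.

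What is at stake is how a null result is read. The unmatched comparison is the confounded one, so readers will look to the matched result. If that shows no difference, it would be presented as coming from a study with 80% power for 15 ml/m², when the pairs actually available may support appreciably less.

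**Working it through.** **Inputs.** From the protocol: difference 15 ml/m², alpha 5%, power 80%, at least 64 per group, 120 patients, 1:1 matching. Assumed because the protocol does not give them: two-sided test, SD, group split, match rate, proportion without a 12-month echocardiogram, within-pair correlation.

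**1. Reproducing 64.** The SD must be back-solved. With SD 30, d = 15/30 = 0.5.

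- Normal approximation: n = 2(1.960 + 0.842)²/0.5² = 62.8, so 63 per group.
- t-test (noncentral t): n = 63.8, so 64 per group; power at 64 is 80.1%.

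So 64 is the plain formula for two equal, complete, independent groups, with no factor for anything else.

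**2. Power by number of pairs.** Two-sample noncentral t with df = 2n − 2 and noncentrality d√(n/2). For 48 pairs this is 0.5 × √24 = 2.449. The detectable difference is SD times the d that gives 80% power.

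| Complete pairs | How it could arise | Power, SD 30 | Detectable difference (ml/m²) |
|---|---|---|---|
| 64 | 64 per group, all matched and complete | 80% | 15.0 |
| 57 | 64 per group, 90% kept | 75% | 15.9 |
| 51 | 64 per group, 80% kept | 71% | 16.8 |
| 60 | 120 enrolled, 50:50, none lost | 77.5% | 15.5 |
| 48 | 120 enrolled, 40:60, none lost | 68% | 17.3 |
| 36 | 120 enrolled, 30:70, none lost | 55% | 20.1 |

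The first three rows respect the floor of 64 in each group; only unmatched or incomplete patients lower them. The last three start from the planned 120, which cannot supply 2 × 64 = 128.

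**3. Adding 10% loss at 120 enrolled.** 60, 48 and 36 pairs become 54, 43 and 32. Power is 73%, 63% and 50%.

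**4. Sensitivity to the SD.** Two-sample t:

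| Pairs | SD 25 | SD 30 | SD 35 |
|---|---|---|---|
| 64 | 92% | 80% | 67% |
| 48 | 83% | 68% | 55% |
| 36 | 71% | 55% | 43% |

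**5. Sensitivity to pairing.** With a paired t-test, df = n − 1 and noncentrality d√(n/(2(1 − r))), where r is the within-pair outcome correlation. For 48 pairs and r = 0.3: 0.5 × √(48/1.4) = 2.93, power 82%. The r needed to regain 80% at SD 30 is about 0.12 with 57 pairs, 0.22 with 51, 0.27 with 48 and 0.46 with 36.

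**6. Keeping everyone.** An unmatched t-test on all 120 has 76% power at 48:72 and 70% at 36:84, against 68% and 55% for the matched pairs. Much of the loss therefore comes from discarding patients, not from the imbalance itself. These two figures ignore confounding and any effect of adjustment on precision.

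**The case against.** There is a fair case on the other side, and several parts of it stand.

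- **The floor.** The protocol asks for at least 64 in each group. If that is met, an unequal split cannot push the smaller group below 64. The 48- and 36-pair cases come from the 120 planned patients; they do not show that meeting the floor would fail. This stands, and with the floor met only match failure and missing data remain.
- **Matching is not labelled primary.** The synopsis also lists a t-test for unrelated samples, which is what 64 per group powers. The choice of primary comparison may sit in an analysis plan not at hand. This stands. Matching is nevertheless the only adjustment named for confounding, and the power statement does not confine itself to the unadjusted test.
- **Pairing may restore power.** True with enough correlation, as step 5 shows. The protocol assumes none, so this gain cannot be counted on.
- **The SD, splits and loss are assumptions.** True. The SD alone moves power as much as the matching does. Figure 1, on how the working sample is formed, is not shown and might say more about the groups.

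A reader might go further and infer that the 80% is simply not delivered. The documents do not support that: 64 complete pairs, or fewer pairs with enough correlation, would keep it. Nor is 64 an arithmetic error; it is correct for d = 0.5. The fault is an omitted allowance.

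**Conclusion.** The concern holds as a gap between the power statement and the planned adjustment. The 80% applies to 64 complete patients per group in an unmatched comparison, and nothing in the design secures the same power once non-randomised groups are matched 1:1, some patients are excluded after surgery, and 120 are enrolled.

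At SD 30, on the calculation's own two-sample basis, power is 71% to 75% if 10% to 20% of 64 per group are lost. With 120 enrolled it is at most 77.5%, falling to 68% or 55% under assumed 40:60 or 30:70 splits. The direction is certain on that basis. The size depends on a back-solved SD, on splits and losses that the protocol does not give, and on ignoring within-pair correlation. Correcting the total to 128 would not settle the matter, because 128 yields 64 pairs only with an exact 64:64 split, every patient matched and every 12-month volume obtained.

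**What to change.** Rewrite the Sample size row of the synopsis, without enlarging the study:

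1. Define what 64 counts: complete matched pairs, or the effective sample size of a weighted or covariate-adjusted analysis that keeps all patients. With pairs, say plainly that 120 patients can give at most 60.
2. State the SD used and its source, and whether the test is one- or two-sided.
3. Replace the unqualified 80% with power and detectable difference for the expected number of complete pairs, over splits from 50:50 to 30:70, a range of SDs, and about 10% missing 12-month echocardiograms. If a paired analysis is intended, state the within-pair correlation assumed.

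The cost is one paragraph and a small table, and a stated power that looks less favourable than the present one. No patients, visits or procedures are added.
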